# 6.4.5 Exploratory Efficacy

#### 6.5 SAFETY ANALYSES

All safety analyses will be performed by dose level in the Phase 1 portion of this study and by cohort in the Phase 2 portion of this study based on the safety analysis set. The incidence of treatment-emergent adverse events (TEAEs) and SAEs will be summarized. Laboratory test results, vital signs, ECG and their changes from baseline will be summarized using descriptive statistics (e.g., n, mean, standard deviation, median, Q1, Q3, minimum, maximum for continuous variables; n [%] for categorical variables). Abnormal values will be flagged.

Safety information will be summarized by phase separately.

# 6.5.1 Dose Limiting Toxicity (Phase 1)

DLTs are taken from the "Dose Limiting Toxicity (DLT)" form on the eCRF. All toxicities or AEs will be graded according to NCI CTCAE version 4.03. A DLT is a toxicity or AE occurring

**Version 1.1**: 02/28/2020 Page 17 of 28

in the first cycle (23 days), which is attributable to pamiparib and meets the criteria defined in Section 4.1.1.2 of the protocol (version 1.1).

All patients will be summarized by type of DLT and by dose level in the DLT Analysis Set.

# 6.5.2 Extent of Exposure

The number (and percentage) of patients requiring dose reductions, dose interruption, and treatment discontinuation will be summarized. One cycle is defined as 21 days of treatment except for the first cycle in the Phase 1 portion of this study.

The duration of treatment (months) will be summarized with descriptive statistics. It will be calculated as (Date of last non-zero dose – Date of first dose + 1) / 30.4375.

Number of patients with dose reductions and treatment discontinuation and their reasons, as well as number of patients with any dose modification will be summarized by counts and percentages according to study medication data. In addition, frequency of dose reductions and dose interruption will be summarized by categories  $(0, 1, \ge 2)$ .

Average dose intensity per patient (in mg/day) and relative dose intensity (total dose received / total dose planned) per patient will be summarized. Average dose intensity is calculated as the total dose (mg) taken by a patient divided by overall duration of exposure (= Date of last non-zero dose – Date of first dose + 1) for individual patient. Relative dose intensity is calculated as the total dose (mg) taken by a patient divided by the total dose planned for the patient by study design. To note, for the Phase 1 portion of the study, the planned dose for a patient will be a single dose on day 1 at a given dose level, no dose on day 2 and then twice daily for the next 21 days for Cycle 1; and then twice-daily for later treatment cycles. Patients in the Phase 2 portion of the study will always be treated on twice-daily administration at the prescribed dose level.

Patient data listings will be provided for all dosing records.

#### 6.5.3 Adverse Events

AEs will be graded by the investigators using CTCAE version 4.03. The AE verbatim descriptions (investigator terms from the CRF) will be classified into standardized medical terminology using MedDRA. Adverse events will be coded to the MedDRA, version 22.0 or higher, lower level term closest to the verbatim term. The linked MedDRA preferred term (PT) and primary system organ class (SOC) are also captured in the database.

A TEAE is defined as an AE that had an onset date on or after the first dose of study drug up to 30 days following study drug discontinuation or was worsening in severity from baseline (pretreatment). All AEs will be included in the listings and only TEAEs will be included in the summary tables. SAEs, deaths, TEAEs with Grade 3 or higher, treatment-related TEAEs and TEAEs that led to treatment discontinuation, dose reduction or dose interruption will be summarized.

Version 1.1: 02/28/2020 Page 18 of 28

An overview table, including the incidence of and the number of patients with TEAEs, treatment-emergent serious adverse events (SAEs), treatment-related TEAEs, TEAEs with Grade 3 or higher, treatment-related treatment-emergent SAEs, TEAEs that led to death, and TEAEs that led to treatment discontinuation, dose reduction or dose interruption will be provided. Treatment-related TEAEs include those events considered by the investigator to be unlikely, possibly or probably or definitely- related to study drug or with missing assessment of the causal relationship.

The incidence of TEAEs will be reported as the number (percentage) of patients with TEAEs by SOC and PT. A patient will be counted only once by the highest severity grade according to CTCAE version 4.03 within an SOC and PT, even if the patient experienced more than 1 TEAE within a specific SOC and PT.

The number (percentage) of patients with treatment-emergent SAEs, treatment-related TEAEs, TEAEs with Grade 3 or higher, treatment-related treatment-emergent SAEs, TEAEs that led to death, and TEAEs that led to treatment discontinuation, dose reduction or dose interruption will be summarized by SOC and PT. TEAEs with grade 3 or higher will also be summarized by PT in descending order.

Patient data listings of all AEs, SAEs, treatment-related AEs, grade 3 or higher AEs, AEs that led to death and AEs that led to treatment discontinuation will be provided.

# 6.5.4 Laboratory Values

Laboratory safety tests (hematology, which is reviewed prior to pamiparib administration, serum chemistry assessed on Day 1 of every cycle, and pregnancy test assessed at screening and EOT) will be assessed in the trial.

Laboratory results will be summarized using Système International (SI) units, as appropriate. For all quantitative parameters listed in Table 3, the actual value and the change from baseline to each postbaseline visit and to the end of treatment will be summarized by visit using descriptive statistics. Qualitative parameters listed in Table 3 will be summarized using frequencies (number and percentage of patients), and changes from baseline to each postbaseline visit and to end of treatment will be reported using shift tables. Percentages will be based on the number of patients with non-missing baseline and relevant postbaseline results. Figures will be provided for better illustration, if needed.

Laboratory parameters will be categorized according to NCI CTCAE version 4.03 grades and shifts from baseline CTCAE grades to maximum and the last postbaseline grades will be assessed. Laboratory parameters will be summarized by worst postbaseline CTCAE grade as well. For the lab tests with both high and low abnormality, separate records of worst CTCAE grade (for high and low) will be generated.

Version 1.1: 02/28/2020 Page 19 of 28

**Clinical Chemistry** Hematology Alanine aminotransferase Hemoglobin (Hgb) Alkaline phosphatase Platelet count White blood cell count Aspartate aminotransferase Albumin Lymphocyte count Bilirubin (total) Neutrophil count Urea Calcium Chloride Creatinine Glucose Lactate dehydrogenase Magnesium Phosphate Potassium

**Table 3. Clinical Laboratory Tests** 

# 6.5.5 Vital Signs

Descriptive statistics for vital sign parameters (systolic and diastolic blood pressure [BP], pulse rate, temperature, and respiratory rate) and changes from baseline for all pre-dose assessments will be presented by visit. Vital signs will be listed by patients, visits and timepoints.

#### 6.5.6 Electrocardiograms

Sodium
Total protein

ECG will be performed at the baseline and multiple time points after the start of treatment. ECG findings at baseline and all other pre-dose assessments on the first of the cycles will be summarized. For triplicated ECG, the averaged value will be used in the summary and additional concentration-QT analysis will be conducted and summarized separately. Patient listing of ECG will be provided for all ECG recordings with the indicator whether the abnormality is clinical significance.

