- 19. Bone ECT scan at baseline is required if the patient has known bone metastases or has symptoms that could be due to bone metastases. The bone ECT test window duration could be expanded to -28 days from -21 days at baseline. In the subsequent visits, whether to conduct bone ECT scan depends on the clinical indication and investigator's decision. Only bone lesion confirmed by CT/MRI or X ray could be recorded as non-target lesion and should be followed with the same method of examination

Procedure									Cy	cle 1									Cycle 2		Cycle 3	
			D	Day 1					Day 2	Day 3	Day 10					Day 1±2		Day 1±2				
Hours	Pre-dose ⁴	0.5	1	2	4	6	9	12 ³	24	481	Pre-dose ⁴	0.5	1	2	4	6	9	12 ³	Pre- dose ⁴	2	Pre- dose ⁴	2
12-lead ECG for PK sampling	X			X ²							Х		X	X	X				X	X	X	X
Vital signs	X	X ²	X^2	X ²	Х	X ¹	Х	X ²	X ²	X ²	X ²	X ²	X ²	X^2	Х	X ²	Х	X ²				
PK sampling	X	X ²	X ²	X ²	Х	X ¹	Х	X ²	X ²	X ²	X ²	X ²	X ²	X ²	Х	X ²	Х	X ²				

Table 6. Pharmacokinetic Sampling in Phase 1 Portion

Abbreviations: ECG, electrocardiogram; PK, pharmacokinetics

General note: It is important that pharmacokinetic (PK) sampling occurs as close as possible to the scheduled time. In order to achieve this, some of the other assessments scheduled at the same time need to be initiated prior to or after the time point to allow for completion of these measurements in enough time for the PK sampling to be taken at the designated time point. Thus, the sequence at a particular time point is: 1) scheduled ECG; 2) vital sign measurements; 3) PK blood samples (to be performed at the precise protocol scheduled time); and 4) any other scheduled or unscheduled measurements at that time point.

1. On Day 3, within 1h before the morning dose

2. For all procedures, a window period of ± 10 minutes exists within 0.5-1h, ± 20 min within 2-4h, ± 30 min within 6-24h after the study drug is taken

3. It should be pre-evening dose

4. The window period is within 1h before morning dose

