- 20. Bone ECT scan at baseline is required if the patient has known bone metastases or has symptoms that could be due to bone metastases. The bone emission computed tomography (ECT) test window duration could be expanded to -28 days from -21 days at baseline. Only bone lesion confirmed by CT/MRI or X ray should be recorded as non-target lesion and should be followed with the same method of examination. If bone metastases are present at screening or if clinically indicated, bone ECT scans should be repeated when a complete response is identified in target lesion or when progression in bone is suspected

1.0

Procedure		Cycle 1 Day 1									Cycle 2 Day 1±3							
Days																		
Hours	Pre- dose	0.5	1	2	4	6	9	12	Pre- dose	0.5	1	2	4	6	9	1		
ECGs ²	X ¹			X ¹					\mathbf{X}^1			X ¹						
Vital signs	X ¹			X^1					\mathbf{X}^1			X ¹						
Serial PK sampling ³	х	Х	Х	Х	Х	Х	Х	X	Х	Х	Х	X	Х	X	X	2		
Sparse PK sampling ⁴	\mathbf{X}^1	1		\mathbf{X}^1					\mathbf{X}^1			\mathbf{X}^1						

Table 8.Pharmacokinetic Sampling in Phase 2 Portion

Abbreviations: ECG, electrocardiogram, PK, pharmacokinetic.

General note: It is important that PK sampling occurs as close as possible to the scheduled time. In order to achieve this, some of the other assessments scheduled at the same time need to be initiated prior to or after the time point to allow for completion of these measurements in enough time for the PK sampling to be taken at the designated time point. Thus, the sequence at a particular time point for serial PK group is: 1) vital sign measurements; 2) scheduled triplicate ECGs; 3) PK blood samples (to be performed at the precise protocol scheduled time, and to be completed within 30 minutes after completion of vital sign measurements, and within 5 minutes after completion of ECG); and 4) any other scheduled or unscheduled measurements at that time point. For sparse PK sampling, the sequence of collection at a particular time point may be determined by the sites based on feasibility.

- The window period is within 1 hour before the morning dose and, ±20 min for the samples 2 hours post dose Note: About 2 mL blood volume will be taken for each sample

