- 2. Triplicate ECGs will be collected from at least 15 patients who contribute to serial PK, with the option to be collected from more patients from sparse PK group, if applicable. Triplicate ECGs for each patient should be obtained from a calibrated machine provided for the study and the same machine must be used for all ECG assessments. The triplicate ECGs results will also be sent to a central reader so that a concentration-QTc analysis can be attempted12-lead ECGs will be performed on the rest of patients who contribute to sparse PK without triplicate ECGs. Triplicate or 12-lead ECGs will be performed on Cycle 1 Day 1 and Cycle 2 Day 1 prior to pamiparib PK assessments.
- 3. Serial PK sampling will be collected on approximately 15 patients on Cycle 1 Day 1 and Cycle 2 Day 1 at time points of pre-dose, 0.5, 1, 2, 4, 6, 9, and 12 hours after study drug is taken. A window period of ± 10 min exists within 0.5-1 hour, ± 20 min within 2-4 hours, ±30 min within 6-12 hours. Serial PK sampling will be collected in this study and only in patients from sites that area able to adequately perform PK sampling, handling, and processing procedures as outlined in the laboratory manual
- 4. Sparse PK sampling will be collected in this study from sites that are able to adequately perform PK sampling, handling, and processing procedures as outlined in the laboratory manual

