#### 6.6 PHARMACOKINETIC ANALYSES

Concentration of pamiparib and PK parameters will be summarized and listed for Phase 1 and Phase 2 separately. Dose proportionality will be assessed for Phase 1 portion. All other PK related analysis like concentration-QTc analysis, PK analysis on renal impairment population, PK analysis on hepatic impairment population, etc. will be presented separately and will not be included in the study-level CSR.

**Version 1.1**: 02/28/2020 Page 20 of 28

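### SAP 6.5.6 summarises only baseline and first-day-of-cycle pre-dose ECGs, so every scheduled post-dose ECG is listed but never tabulated in the study report.

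*SAP*

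**What the plan says.** SAP 6.5 opens with a general statement: "Laboratory test results, vital signs, ECG and their changes from baseline will be summarized using descriptive statistics". It names no time points. SAP 6.5.6 is the specific rule: "ECG findings at baseline and all other pre-dose assessments on the first of the cycles will be summarized". The same section continues: "For triplicated ECG, the averaged value will be used in the summary and additional concentration-QT analysis will be conducted and summarized separately". It closes with a listing: "Patient listing of ECG will be provided for all ECG recordings with the indicator whether the abnormality is clinical significance". SAP 6.6 says that the concentration-QTc work, with other further PK analyses, "will be presented separately and will not be included in the study-level CSR".

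The protocol collects more than the SAP tabulates. Table 6 has a Phase 1 row, "12-lead ECG for PK sampling", with pre-dose and post-dose entries. Table 8 places Phase 2 ECGs at pre-dose and 2 hours, with a timing tolerance stated as "20 min for the samples 2 hours post dose". Its second footnote adds: "Triplicate or 12-lead ECGs will be performed on Cycle 1 Day 1 and Cycle 2 Day 1 prior to pamiparib PK assessments".

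ECG change is part of the Phase 1 primary endpoint (SAP 4.1.1) and is a Phase 2 secondary endpoint (SAP 4.2.2).

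**The concern.** The rule confines the ECG tables to trough or drug-free values. In Phase 2 the Cycle 1 Day 1 pre-dose ECG precedes any drug. Table 7 schedules no other routine ECG during treatment, so the Cycle 2 Day 1 trough is the only scheduled on-drug PK-day ECG that is summarised.

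The protocol treats QTcF around 500 msec, or a change around 60 msec, as important (Table 9 and Section 7.3.3.1). SAP 6.5.6 plans no count of patients who cross either threshold. Laboratory data, by contrast, get worst-postbaseline-grade and shift tables (SAP 6.5.4).

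What is at stake is a QTc shift that follows dosing but is too small to be reported as an event. A reader of the study report would have no mean change and no patient count from which to see it.

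**Working it through.** The check sets the protocol's ECG schedule against the SAP rule. The plan states no figure of its own to reproduce.

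**Inputs.** Phase 1: protocol Table 6. Phase 2: protocol Table 8. Rule: SAP 6.5.6, read as pre-dose on the first day of a cycle.

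| Visit | Scheduled ECGs | Pre-dose | Post-dose | Summarised |
|---|---|---|---|---|
| Phase 1, C1D1 | pre-dose, 2 h | 1 | 1 | 1 |
| Phase 1, C1D10 | pre-dose, 1, 2, 4 h | 1 | 3 | 0 |
| Phase 1, C2D1 | pre-dose, 2 h | 1 | 1 | 1 |
| Phase 1, C3D1 | pre-dose, 2 h | 1 | 1 | 1 |
| **Phase 1 total** | **10** | **4** | **6** | **3** |
| Phase 2, C1D1 | pre-dose, 2 h | 1 | 1 | 1 |
| Phase 2, C2D1 | pre-dose, 2 h | 1 | 1 | 1 |
| **Phase 2 total** | **4** | **2** | **2** | **2** |

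- Phase 1 points not summarised: 10 − 3 = 7, of which 6 are post-dose and 1 is the Day 10 pre-dose ECG.
- Phase 2 points not summarised: 4 − 2 = 2, both post-dose. This applies only to patients at sites able to do PK sampling.
- Post-dose points summarised: 0 of 6 + 2 = 8.

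The literal wording also leaves out end-of-treatment ECGs.

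**How far could a trough value understate an effect?** Protocol 1.4.1 gives a half-life of about 13 h (range 5.4 to 34 h) in the first-in-human study. Assume mono-exponential decline from 2 h to the next dose at 12 h. The 12 h concentration as a fraction of the 2 h value is then 0.5^(10/half-life):

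- 13 h: 0.5^(10/13) = 0.59
- 5.4 h: 0.5^(10/5.4) = 0.28
- 34 h: 0.5^(10/34) = 0.82

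The steady-state means from this trial's Phase 1 point the same way. AUC0-9 divided by 9 h, as a fraction of Cmax, is:

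- 20 mg: 9361/9/1450 = 0.72
- 40 mg: 33545/9/5340 = 0.70
- 60 mg: 39657/9/6048 = 0.73

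The profile is therefore fairly flat. Under these assumptions, trough exposure is typically a little over half of the 2 h level, and it may be much less in a patient with a short half-life.

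**The case against.** The strongest reply is that a large effect already has a route into the report. Under Table 9, QTc values beyond the thresholds lead to a hold, and to discontinuation if a cardiologist confirms them. Protocol 9.1.5 has ECG abnormalities judged clinically significant recorded as adverse events, and in general counts those that lead to interruption or discontinuation. SAP 6.5.3 then tabulates TEAEs, including those leading to interruption or discontinuation. This stands, although the step depends on the investigator's judgement. A reader might infer that a QTc effect after dosing would be absent from the safety tables altogether. The documents do not support that.

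A reader might also infer that the omitted ECGs are the near-peak ones. The documents describe rapid absorption but give no Tmax value, and they do not say the ECGs were timed to the peak. Only the term post-dose is supported. Nor are the data discarded: every recording is listed with a clinical-significance indicator, and the triplicates feed the separate concentration-QTc analysis.

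Three further points lower the urgency. Trough exposure is not negligible, as shown above. The protocol reports no apparent hERG inhibition and no QT prolongation in dogs (1.3.1). Phase 1 had 15 patients (4, 4 and 7 by dose), few enough to review from a listing. Pre-dose-only tables are also the SAP's convention for vital signs (6.5.5).

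Finally, SAP 6.5 and the triplicate sentence in 6.5.6 could be read more loosely, since neither repeats the pre-dose limit. But no text provides for a post-dose summary, and 6.5.6 is the specific rule.

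**Conclusion.** The concern holds as a weakness in the safety summary. As written, no scheduled post-dose ECG reaches a study-report summary table: 6 of 10 PK-matched time points in Phase 1 and 2 of 4 in Phase 2 patients with PK sampling are post-dose. Counting the Day 10 pre-dose ECG, 7 of 10 Phase 1 points are not summarised. The one analysis that would use post-dose ECGs sits outside the report. The protocol asks for its triplicates from at least 15 patients and says only that the analysis can be attempted.

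The consequence is limited. A post-dose QTc shift below the level at which an investigator reports an event could be attenuated or missed in trough-only tables. Larger effects can reach the adverse event tables.

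The counts rest on Tables 6 and 8 and a literal reading of the SAP rule. The trough fractions rest on the stated half-lives and an assumed mono-exponential decline. The action is worth taking because ECG change belongs to a Phase 1 primary and a Phase 2 secondary endpoint.

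**What to change.** In SAP 6.5.6:

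- Summarise QTcF and its change from baseline (the last value before first dose, SAP 6.2.1) at every scheduled pre- and post-dose time point. Use triplicate means where available. Present by dose level in Phase 1 and by cohort in Phase 2.
- Add the number of patients with any postbaseline QTcF beyond 500 msec, or any increase beyond 60 msec. These thresholds come from the protocol.
- State the inequality used for these counts. Table 9 uses strictly greater than, while Section 7.3.3.1 uses greater than or equal to. The two passages must be reconciled. This affects only how patients are counted here and implies no view on which management rule is right.

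If leaving post-dose ECGs out of the tables is deliberate, the SAP should at least say that they are reported only in listings and in the separate concentration-QTc report.

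The cost is a few extra tables from data already collected, with no new visits or procedures. Numbers per dose level in Phase 1 will be small.

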#### **6.5.7 ECOG Performance Status**

ECOG scores will be summarized by visit.

#### 6.6 PHARMACOKINETIC ANALYSES

Concentration of pamiparib and PK parameters will be summarized and listed for Phase 1 and Phase 2 separately. Dose proportionality will be assessed for Phase 1 portion. All other PK related analysis like concentration-QTc analysis, PK analysis on renal impairment population, PK analysis on hepatic impairment population, etc. will be presented separately and will not be included in the study-level CSR.

**Version 1.1**: 02/28/2020 Page 20 of 28

#### 6.6.1 Phase 1 Portion

# **PLASMA CONCENTRATIONS**

For Phase 1 portion, plasma samples for pamiparib will be collected on Cycle 1 Day 1, 2 and 3 after a single dose and on Cycle 1 Day 10, Cycle 2 Day 1 and Cycle 3 Day 1 during BID dosing. Pharmacokinetic blood sampling time points will occur at pre-dose, then at 0.5, 1, 2, 4, 6, 9, 12, 24 and 48 hours post first dose, pre-dose, 0.5, 1, 2, 4, 6, 9 and 12 hours postdose on Cycle 1 Day 10, and predose, 2 hours postdose on Cycle 2 Day 1 and Cycle 3 Day 1.

Plasma pamiparib concentration-time data will be summarized and displayed in both tabular and graphical form. Concentration-time data will be analyzed with standard non-compartmental and/or compartmental methods. Pharmacokinetic concentration data for pamiparib will be listed including the dose level, relative time to dosing, actual sample collection time. The concentration data will also be summarized with descriptive statistics for each time point by dose level. The number of patients with non-missing plasma concentration, mean, standard deviation, minimum, median, maximum, geometric coefficient of variation and geometric mean will be included in the summary.

The following figures will be provided:

- Individual patient's plasma concentration profiles will be plotted over time on linear scale.
- Individual patient's plasma concentration profiles will be plotted over time on semi-log scale.
- Mean of pamiparib plasma concentration on linear scale will be plotted over time by dose level.
- Mean of pamiparib plasma concentration on semi-log scale will be plotted over time by dose level.

